3.6 Safety Analyses

The analyses will be based on the As-treated population. All safety summaries will be presented by treatment group for each cohort, unless otherwise specified.

3.6.1 Adverse Events and Serious Adverse Events

Adverse events (AE) will be coded by MedDRA version 20.0 or higher. Analysis of adverse events will include the type, incidence, severity and relationship to study investigational product summarized by MedDRA System Organ Class (SOC) and Preferred Term (PT) by treatment group for each cohort as well as for overall treatments. The AEs summaries will include only treatment-emergent AEs, i.e., those occurring after initial receipt of investigational product. Subjects will be counted once for specific PT or MedDRA SOC when calculating incidence. If the same AE Preferred Term occurs multiple times within a subject, the highest severity and level of relationship observed will be reported. Non treatment-emergent AEs/serious adverse events (SAEs) will be presented in the listings.

The number and percentage of subjects with nausea, vomiting, and either nausea or vomiting will be summarized daily for first 7 days of treatment. For MEDI0382 only, the above three endpoints over the first 7 days for two cohorts combined will be summarized. In addition, two-sided 80% confidence intervals of the percentages will also be reported using exact method.

[REDACTED]

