2.3 Exploratory Objectives

Table 2.3-1 Exploratory Objectives and Associated Endpoints

Type	Objective	Endpoint
Safety	To assess gastrointestinal tolerability across different titration schedules (Cohorts 1 and 2)	
 Percentage of subjects with gastrointestinal AEs at each dose level Percentage of subjects with nausea and vomiting from baseline (Day 1) over 7 days of treatment
PD	To assess the effect of MEDI0382 on glucose lowering during different meals and times of the day as measured by continuous glucose monitoring (CGM) (Cohort 1 only)	
 Change in percentage of time in hyperglycaemia (defined as > 7.8 mmol/l or > 140 mg/dl) and hypoglycaemia (defined as < 3 mmol/l or < 54 mg/dl) from baseline (Day -1) over 24 hours to the end of dosing at each dose level (Days 7, 14, 21, 28, and 49) Change in percentage of time in hyperglycaemia (defined as > 7.8 mmol/l or > 140 mg/dl) and hypoglycaemia (defined as < 3 mmol/l or < 54 mg/dl) over 7 days at each dose level (Days 1 to 7, Days 8 to 14, Days 15 to 21, and Days 22 to 28) Change in glucose AUC_{120min} during a standardised meal in the morning from baseline (Day -1) and at the end of 49 days of treatment Change in glucose AUC_{120min} during a standardised meal in the evening from baseline (Day -1) and at the end of 49 days of treatment
Efficacy	To characterise the effect of MEDI0382 on glucose lowering and weight versus placebo after 7, 14 and 49 days (Cohort 2 only)	
 Percentage change in glucose AUC as measured by a standardised MMTT from baseline (Day -1) after 14 and 49 days Change in fasting plasma glucose from baseline (Day -1) to the end of 7, 14, and 49 days of treatment Percentage and absolute change in body weight from baseline (Day 1) to the end of 7, 14, and 49 days of treatment Change in HbA1c from baseline (Day -1) to the end of 49 days of treatment

Table 2.3-1 Exploratory Objectives and Associated Endpoints

Type	Objective	Endpoint
PD	To assess the effect of MEDI0382 on ketone bodies, amino acids, and free fatty acid (FFA) levels over 49 days of treatment (Cohort 1 only)	
 Change in plasma beta-hydroxybutyrate from baseline (Day -1) while fasted and at 4 hours postdose after 49 days Change in FFA levels from baseline (Day -1) after 49 days of treatment Change in amino acid levels from baseline (Day -1) after 49 days of treatment

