4 MATERIALS AND METHODS

4.1 Subjects

4.1.1 Number of Subjects

Enrollment of up to 63 subjects across multiple study sites is planned, 39 subjects in Cohort 1 (26 subjects to receive MEDI0382 and 13 to receive matched placebo) and 24 subjects in Cohort 2 (18 subjects to receive MEDI0382 and 6 subjects to receive matched placebo).

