4.8.3.3 Exploratory Analyses

For analyses of the exploratory endpoints (Section 2.3), an ANCOVA model similar to the primary efficacy analysis will be used for continuous endpoints. For proportion-related endpoints, a logistic regression model will be used with fixed effects of treatment and baseline measurement.

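### The visible SAP text gives the first-7-day nausea and vomiting incidence for MEDI0382 only; a matching pooled placebo column would cost almost nothing

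*SAP*

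**What the plan says.** Protocol section 2.3 lists, under an exploratory gastrointestinal tolerability objective covering both cohorts, the endpoint "Percentage of subjects with nausea and vomiting from baseline (Day 1) over 7 days of treatment". Nothing in it confines the endpoint to active subjects. Protocol section 4.8.3.3 then says how exploratory proportions are to be analysed: "For proportion-related endpoints, a logistic regression model will be used with fixed effects of treatment and baseline measurement".

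SAP section 3.6.1 plans two first-week outputs:

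- A daily table: "The number and percentage of subjects with nausea, vomiting, and either nausea or vomiting will be summarized daily for first 7 days of treatment". Under the default in SAP section 3.6, "All safety summaries will be presented by treatment group for each cohort, unless otherwise specified", this table includes placebo, split by cohort.
- A cumulative summary: "For MEDI0382 only, the above three endpoints over the first 7 days for two cohorts combined will be summarized". The sentence that follows adds that "two-sided 80% confidence intervals of the percentages will also be reported using exact method".

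The general adverse event tables in SAP section 3.6.1 are by treatment group within cohort and for overall treatments, counting each subject once per term. The visible text does not limit them to the first week. Protocol section 4.8.4 adds subject-level listings of all adverse events. A redacted paragraph comes directly after the sentences quoted from SAP section 3.6.1.

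**The concern.** Days 1 to 7 are the one window in which every active subject in both cohorts is scheduled to receive the same 50 µg starting dose (protocol section 3.1.2). Finding a schedule that reduces gastrointestinal events is one of the study's three stated purposes (protocol section 1.5), and the lower starting dose is part of that strategy (protocol section 3.2.3.3). The pooled first-week percentage is therefore a figure that readers will pick out.

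Shown for MEDI0382 alone, it cannot be separated from background. Readers would tend to set it against the 27% and 42% nausea rates from the prior study in protocol section 3.2.3.3. Those come from groups of 11 and 12 subjects who started at 100 µg on other schedules. A concurrent randomised control is available in this trial, because the two cohorts recruit in parallel and each has its own placebo arm.

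**Working it through.** **1. Denominators.** Protocol section 4.1.1 gives Cohort 1 as "26 subjects to receive MEDI0382 and 13 to receive matched placebo", and Cohort 2 as 18 and 6.

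- Active: 26 + 18 = 44
- Placebo: 13 + 6 = 19

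Both match the combined arm sizes in the sample-size text (protocol synopsis; SAP section 2.4). These are planned numbers; protocol section 4.1.7 allows up to five replacements per cohort. The documents state no power or precision for this endpoint, so there is no other figure to reproduce.

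**2. What each planned output gives for placebo.**

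| Output | Placebo shown? | Window | Gives 7-day subject incidence? |
|---|---|---|---|
| Daily table | Yes, n=13 and n=6 | Each day, Days 1–7 | No |
| Cumulative summary | No | Days 1–7 | Active arm only |
| General AE tables | Yes | Whole study | No |
| AE listings | Yes | Whole study | Only by hand count |

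**3. Why daily rows do not give the 7-day figure.** Let d_k be the number of placebo subjects affected on day k, and C the number affected at least once in the week. Then

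max(d_k) ≤ C ≤ min(n, Σ d_k).

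Suppose one Cohort 1 placebo subject is affected on each of the seven days. Then 1 ≤ C ≤ 7, so the pooled incidence lies between 1/19 = 5.3% and 7/19 = 36.8%. The whole-study count W adds the cap C ≤ W. That can narrow the range, but it fixes C only if W happens to equal the lower bound.

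**4. Precision with and without pooling.** The exact (Clopper-Pearson) 80% limits are the 0.10 quantile of Beta(x, n−x+1) and the 0.90 quantile of Beta(x+1, n−x). For x = 0 the upper limit is 1 − 0.10^(1/n):

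- n=6: 31.9%
- n=13: 16.2%
- n=19: 11.4%

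**5. Illustration. All event counts are assumed.**

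| Arm | Count | Percentage | Exact 80% CI |
|---|---|---|---|
| MEDI0382 | 9/44 | 20.5% | 12.7 to 30.4 |
| Placebo, case a | 0/19 | 0% | 0 to 11.4 |
| Placebo, case b | 2/19 | 10.5% | 2.8 to 25.7 |
| Placebo, case c | 4/19 | 21.1% | 9.5 to 37.8 |

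The same active figure would look mainly drug-related beside case a and like background beside case c. The planned cumulative summary cannot tell these cases apart.

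**6. What a difference would offer.** The 80% half-width is 1.2816 × √(p₁(1−p₁)/44 + p₀(1−p₀)/19). The active rates are borrowed from the prior study, and the placebo rates are assumptions.

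- 27% vs 5%: 1.2816 × √(0.00448 + 0.00250) = 10.7 points
- 42% vs 10%: 1.2816 × √(0.00554 + 0.00474) = 13.0 points

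Exact Fisher power for these two cases is about 50% and 72% at two-sided 0.05, and 66% and 84% at two-sided 0.10. The comparison is informative for description but not strongly powered.

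**7. Why by-cohort rows should stay.** Allocation is 2:1 in Cohort 1 and 3:1 in Cohort 2. Cohort 1 therefore supplies 26/44 = 59.1% of the pooled active subjects but 13/19 = 68.4% of the pooled placebo subjects. A crude pooled contrast weights the cohorts differently in the two arms.

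**The case against.** The best defence is that the objective concerns tolerability across titration schedules. Where the protocol wants a placebo contrast, it says so: in the primary objective, the 50 µg glucose objective and the Cohort 2 efficacy objective. Pooling active subjects while they share a dose gives one rate for that purpose, and the endpoint is exploratory and descriptive. This stands as a limit on severity. It does not explain the restriction, because the endpoint itself names no arm and protocol section 4.8.3.3 puts treatment in the model for exploratory proportions.

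A second defence is that placebo information is not lost. That is correct. A reader might infer that the plan leaves no first-week placebo data, or that the endpoint can never be obtained for placebo. The documents do not support either reading: placebo is in the daily table, the whole-study tables cap the figure, and the listings would let someone count it. What is absent from the visible text is one tabulated summary.

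Third, the redacted paragraph may hold further gastrointestinal analyses, and table specifications sit in a separate programming plan (SAP section 1). Neither can be checked, so no claim about the full plan is possible.

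Finally, 19 placebo subjects are few, and the documents give no placebo nausea rate. Both are true. But the SAP already combines the cohorts by treatment for the Day 7 glucose AUC (section 3.4.2.2), so pooling placebo for the same week follows its own practice.

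**Conclusion.** The point holds for the visible text. The SAP specifies the cumulative first-week incidence for pooled MEDI0382 only, which is narrower than the protocol endpoint and omits the treatment effect that the protocol assigns to exploratory proportions. No other visible table supplies the 7-day placebo incidence.

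The consequence is moderate. The gap affects how an exploratory percentage is read, not any primary or secondary test, and the data are collected and listed. The denominators are planned numbers. The 5.3% to 36.8% range illustrates an indeterminacy and is not a forecast. All event counts and placebo rates in the calculations are assumptions, so nothing here shows that the active rate would be overstated or by how much.

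**What to change.** In SAP section 3.6.1, delete the restriction to MEDI0382. Report nausea, vomiting and either event over the first 7 days for pooled MEDI0382 (planned n=44) and pooled placebo (planned n=19) side by side, with the same exact 80% intervals. Keep by-cohort rows because the allocation ratios differ.

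A treatment difference, ideally taking account of cohort, or the logistic model of protocol section 4.8.3.3, is an optional descriptive addition. If the model is not wanted, one sentence in the SAP should record the departure from the protocol. If the redacted text or the programming plan already provides the placebo figure, a cross-reference is enough.

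The cost is one SAP sentence and one table column. No new data, visits or subjects are needed.

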3.6.2 Adverse Events of Special Interest

Hepatic function abnormality meeting the definition of Hy's law is considered an adverse event of special interest. Number and proportion of subjects who meet Hy's law criteria: AST or ALT $\geq 3 \times$ ULN together with total bilirubin $\geq 2 \times$ ULN will be summarized by treatment and cohort.

3.6.3 Deaths and Treatment Discontinuations due to Adverse Events

Death and AEs resulting in permanent discontinuation from the study drug will be summarized by treatment and cohort. The summary includes overall, categorized by MedDRA system organ class, and preferred term.

3.6.4 Clinical Laboratory Evaluations

Hematology, serum chemistry, and urinalysis laboratory evaluations will be performed during the study. The hematology and serum chemistry (including calcitonin, lipase, and amylase) parameters as well as their changes from baseline will be summarized with descriptive statistics (number of subjects, mean, and standard deviation, median, minimum and maximum) by treatment group at each of the time points specified in Treatment and Follow-up Period Study Procedures in the protocol. The urinalysis results will be listed. The hematology and serum chemistry results will also be classified as low, normal, or high. The urinalysis results will be classified as normal or abnormal. The shift from baseline hematology, serum chemistry, and urinalysis results will be summarized by treatment group at each of specified time points.

3.6.5 Vital Signs

Vital signs including pulse rate (beats/min), systolic and diastolic blood pressure (mmHg), temperature ($^{\circ}$ C), weight (kg), and respiratory rate (breaths/min), as well as the change from baseline for each of those parameters will be descriptively summarized by treatment group at each of the specified time points in the protocol.

The 24-hour average ambulatory blood pressure monitoring (ABPM) pulse rate (beats/min) and systolic and diastolic blood pressure (mm Hg) from the ABPM will be summarized by treatment group at each visit (Days -2, 22, 29, 36, 43, and 49) performed. The change from baseline (Day -2) for the 24-hour average pulse rate and systolic and diastolic blood pressure at each post-baseline visit will be analyzed with an ANCOVA with an effect for treatment and the baseline value as the covariate. The above summary and analyses will also be conducted for PR, SBP and DBP during asleep and awake periods.

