Subjects will undergo blood tests for safety between Day -7 and Day -3 if the screening visit was more than 7 days before dosing begins on Day 1. On Day -2, subjects will be admitted to the clinical unit for 2 nights and will undergo further initial safety assessments and training in subcutaneous (SC) injection administration. At this time an ambulatory blood pressure monitoring (ABPM) device will be fitted on Day -2 and worn for 24 hours; simultaneously a CGM sensor will be fitted on the contralateral arm and the subject will be given training for CGM use, and subjects will be expected to wear CGM sensors continuously until the end of dosing. On Day -1, eligibility criteria will be verified and subjects will undergo 2 MMTT assessments (MMTT type A; with blood sampling in the morning and MMTT type C; without blood sampling in the evening). Subjects can be randomised at any time after confirming eligibility from Day -1 to Day 1 (predose) to receive either MEDI0382 or placebo. On Day 1, dosing will commence following predose safety measures including vital signs, blood tests for safety, an ECG, and measurement of weight. Since the dose of 50 µg will require a dilution by site staff prior to administration, subjects will have the option to remain as an inpatient or alternatively attend the clinical unit every day for dosing during the first week, and during this time will undergo supervision to self-administer the investigational product. On Day 7, safety

assessments will be performed and the MMTT will be repeated, and where relevant, subjects will be discharged home.

Subjects will then return to the clinical unit at weekly intervals until a maintenance dose of 300 µg is achieved. On Day 22, subjects will be readmitted to the clinical unit for an overnight stay to undergo PK sampling and ABPM for 24 hours. Subjects will be discharged on Day 23 and will thereafter attend for weekly visits for safety assessments and ABPM device fitting. At the end of dosing, subjects will be readmitted to the clinical unit for a final overnight stay and MMTTs type A and C will be repeated alongside safety assessments, ABPM, weight measurement, and blood tests. A 7- to 14 day post-last dose follow-up visit and final follow-up visit approximately 28 days after the last dose will be performed for safety assessments and this will include a final ABPM recording.

Cohort 2

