Subjects will then return to the clinical unit at weekly intervals until a maintenance dose of 300 µg is achieved. On Day 22, subjects will be readmitted to the clinical unit for an overnight stay to undergo PK sampling and ABPM for 24 hours. Subjects will be discharged on Day 23 and will thereafter attend for weekly visits for safety assessments and ABPM application. At the end of dosing, subjects will be readmitted to the clinical unit for a final overnight stay, and an MMTT (Type A) will be repeated alongside safety assessments, ABPM, measurement of weight, and blood tests. A second MMTT (Type C) without serial blood sampling will be performed on the evening of Day 49 and an HbA1c and exploratory biomarkers will be repeated. A 7- to 14-day post-last dose follow-up visit and final follow-up visit approximately 28 days after the last dose will be performed for safety assessments, and a final ABPM recording will be made at this time.

Cohort 2

Study procedures for Cohort 2 will be similar to Cohort 1 at baseline, although subjects will not undergo ABPM assessments nor wear a CGM monitor in this cohort. [REDACTED]

[REDACTED]
[REDACTED]
[REDACTED] Safety bloods will be performed at anytime from Day -7 to Day -3 if the screening visit was more than 7 days before Day 1 (Figure 3.1.1-1). Subjects may be confined to rest for the duration of the breath test period. On admission to the clinical unit on Day -2, subjects will undergo further baseline safety assessments and undergo their first MMTT (Type A) with serial blood sampling on Day -1. Dosing will commence on Day 1. Since the dose of 50 µg will require a dilution by site staff prior to administration, subjects will be given the option to either remain as an inpatient, or attend the clinical unit every day during the first 2 weeks of dosing, but will be required to stay overnight for a total of 5 nights across this period (on Days -2, -1, 1, 7, and 14); thereafter, subjects will attend the unit for dose up-titration. During this time subjects will self-administer investigational product under supervision. [REDACTED] and MMTTs (Type B) with serial blood sampling will be repeated at different points across the study as described in the schedule. At the end of dosing on Day 49, subjects will be admitted for a final overnight stay; a repeat MMTT (Type A) will be performed, alongside measurement of weight and safety assessments. [REDACTED]

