3.2.3.2 Secondary Endpoints

Additional Measures of Glucose Lowering and Weight Loss

In order to better characterise the glucose-lowering efficacy of MEDI0382 up to 300 µg across 49 days of dosing, additional markers of glucose control including HbA1c and fasting glucose level will be measured, alongside exploratory measures of glucose control generated by CGM. Absolute change in weight will also be measured and the proportion of subjects achieving clinically significant weight loss (> 5% of body weight) will be recorded.

In evaluating the 50 µg dose of MEDI0382, this study will determine if repeat administration of 50 µg is more effective than placebo with respect to glucose lowering at 7 days through measurement of glucose AUC during a standardised MMTT. Results from the prior multiple-ascending-dose study (Study D5670C00002) of MEDI0382 on glucose AUC reduction have shown a reduction of 41.8% after 7 days at 100 µg, 36.7% after 11 days at 150 µg following up-titration from 100 µg, and 39.6% after 15 days at 200 µg following up-titration from 100 µg and 150 µg. Results from this previous study will be used as a benchmark to further evaluate the results.

Safety and Tolerability

In prior studies (Study D5670C00002), 300 µg of MEDI0382 has been administered to 23 obese and overweight subjects with T2DM for 7 days after 2 up-titration steps, and was shown to have an acceptable tolerability and safety profile over this period of dosing. During treatment, there was no significant increase in systolic or diastolic BP, but a significant increase in heart rate of 6.6 beats per minute (90% CI 4.1, 9.1) was recorded after 7 days of dosing (Cohorts 5 and 6 pooled data; n = 19). In the cohorts that received MEDI0382 up-titrated to 300 µg, nausea and vomiting were observed in a maximum of 41.7% (Cohort 6) and 27.3% (Cohort 5) of subjects, respectively. Safety and tolerability with greater exposure at the 300 µg dose level will be measured with safety laboratory tests, ABPM recording of heart rate and BP and other vital signs, and recording of AEs.

Pharmacokinetic Profile and Immunogenicity

Plasma concentrations of MEDI0382 at 50 and 300 µg will be used to evaluate the PK profile (C_{max} , time to maximum concentration [T_{max}], AUC_{tau} , and $C_{min}[R_0]$ [accumulation ratio]). In addition, C_{trough} at other dose levels will be evaluated to establish steady state achievement.

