Note: Whenever vital signs, ECGs, and blood draws are scheduled for the same nominal time, the ECG should occur first, then vital signs, and blood draws should occur last. The timing of the ECGs and/or vital signs should be such that it allows the blood draw (eg, for PK and PD) to occur as close as possible to the scheduled time. Ten minutes of supine rest should precede these assessments.

- a The eligibility check should be based on all clinical measurements and blood tests taken during the screening visit (V1) with the exception of eGFR, liver function tests, blood pressure, urinary illicit drug, alcohol and pregnancy tests, which should be rechecked on Day -2. A targeted physical examination and repeat medical history should also be undertaken to ensure the subject is well enough to commence dosing.
- b The diet of subjects should not be restricted in any way during the study (including during inpatient stay) unless fasting or a standardised meal is specified.
- c Subjects who prefer to attend for daily visits during the first week will be discharged home on Day 1 after all assessments are complete. (X) indicates that subjects can be inpatients or outpatients at these visits.
- d A serum or urine pregnancy test should be conducted on any female subject of childbearing potential as detailed in the schedule. Pregnancy tests do not need to be conducted in women who are surgically sterile (ie, bilateral tubal ligation, bilateral oophorectomy, or complete hysterectomy) or are postmenopausal (defined as at least 1 year since last menses and having an elevated follicle stimulating hormone laboratory value which is in the postmenopausal range in previous laboratory test results).
- e Vital Signs Schedule (blood pressure, heart rate, respiratory rate, and temperature): on days where ABPM is due to be checked a predose set of vital signs should be performed prior to application of the ABPM cuff. Blood pressure should be measured once at heart level in the nondominant arm where possible, opposite to the arm where the CGM device is applied, after the subject has rested in either a seated or supine position for at least 10 minutes. For time points where ECG recording precedes vital sign measurement, the 10-minute rest in the supine position prior to the ECG suffices for the rest prior to vital sign measurement.
 - o Day -2; vital signs to be taken prior to fitting the ABPM device; postural (standing and supine) blood pressures should be performed at this time.

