4.2.3 Follow-up Period

Table 4.2.3-1 shows all procedures to be conducted during the follow-up period.

Whenever vital signs, 12-lead ECGs, and blood draws are scheduled for the same nominal time, the assessments should occur in the following order: 12-lead ECG, vital signs, and then blood draws.

After the end of the follow-up period, subjects will return to the care of their own physicians according to local requirements and local standards.

Table 4.2.3-1 Schedule of Follow-up Procedures

Study Period	Follow-up Period
Visit Number	Final
Procedure/Study Day	28 days post last dose (\pm 3 days)
Targeted physical examination	X
Weight	X
ECG	X
Vital signs (BP, heart rate, body temperature, RR) ^a	X
ABPM (Cohort 1 only)	X
	
Serum chemistry panel	X
Fasting lipid profile	X
Calcitonin ^c	X
Haematology	X
Urinalysis	X
HbA1c	X
Pregnancy test	X
MEDI0382 ADA ^d	X
Assessment of AEs/SAEs	X
Concomitant medications	X

ABPM = ambulatory blood pressure monitoring; AE = adverse event; ADA = anti-drug antibody; BP = blood pressure; ECG = electrocardiogram; HbA1c = glycated haemoglobin; min = minute; RR = respiration rate; SAE = serious adverse event; ULN = upper limit of normal

- ^a Blood pressure should be measured once at heart level in the nondominant arm where possible, after the subject has rested in either a seated or supine position for at least 10 minutes.
- ^b Subjects should fast for > 10 hours the night before; in the morning, a baseline blood test for glucose and insulin should be taken alongside a baseline measurement of expired CO₂ just prior to administration of C¹³- octanoate in conjunction with a standardised solid meal. Subjects will be expected to consume the meal within less than 5 minutes. Blood sampling of glucose and insulin should be performed at t = 0

Table 4.2.3-1 Schedule of Follow-up Procedures

Study Period	Follow-up Period
Visit Number	Final
Procedure/Study Day	28 days post last dose (± 3 days)

(baseline), t = 30 min, t = 60 min, t = 120 min and t = 240 min (± 5 min) after taking the standardised meal. Concurrent sampling of expired CO₂ should occur as described in the detailed methods section.

^c Only to be repeated if the calcitonin level was > ULN in the sample taken at the end of dosing

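### SAP section 3.6.5 leaves the protocol's 28-day follow-up ABPM recording out of the visits to be summarised and modelled

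*SAP*

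**What the plan says.** **Protocol, collection.** For Cohort 1, section 3.1.1 describes the post-treatment visits and states that "a final ABPM recording will be made at this time". The synopsis agrees: "this will include a final ABPM recording". Both sentences mention the 7- to 14-day visit and the 28-day visit before the recording. Table 4.2.3-1 (section 4.2.3) settles which is meant: its row "ABPM (Cohort 1 only") is marked at the final visit, 28 days after the last dose with a window of 3 days either side.

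**Protocol, objective and analysis.** Table 2.2-1 sets a secondary objective on safety and tolerability during dosing and follow-up. 24-hour heart rate and blood pressure is the first measure it names. Section 4.8.4.1 plans an ANCOVA of the 24-hour means at different time points, adjusted for baseline. It does not exclude follow-up.

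**SAP.** Section 3.6.5 summarises the 24-hour averages by treatment group "at each visit (Days -2, 22, 29, 36, 43, and 49) performed". The next sentence says that the change from Day -2 "at each post-baseline visit will be analyzed with an ANCOVA with an effect for treatment and the baseline value as the covariate". The same summaries and models are then extended to the asleep and awake periods. No other SAP section summarises or models ABPM.

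**The concern.** Subjects in Cohort 1 wear a cuff for a further 24 hours about four weeks after the last dose, and the SAP gives that recording no table and no model. The measure matters to this programme. Protocol section 3.2.3.2 reports from the earlier study that "a significant increase in heart rate of 6.6 beats per minute (90% CI 4.1, 9.1) was recorded after 7 days of dosing", and names ABPM among the tools for assessing longer exposure at 300 µg. Whether a heart-rate change persists after treatment stops belongs to the follow-up half of the safety objective, and this is the only 24-hour recording made after treatment. If the SAP is programmed as written, the study report would have no prespecified ABPM result for that period. Any such result would have to be added after unblinding.

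**Working it through.** The plan states no figure on this point, so there is none to reproduce. The main check is a comparison of two visit lists.

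**1. Visit lists**

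| ABPM time point | Protocol source | In SAP 3.6.5 list |
|---|---|---|
| Day -2 | Table 4.2.2-1, footnote e: "Day -2; vital signs to be taken prior to fitting the ABPM device" | Yes |
| Days 22, 29, 36, 43 | same footnote | Yes |
| Day 49 | same footnote | Yes |
| 28 ± 3 days after last dose | Table 4.2.3-1; section 3.1.1; synopsis | **No** |

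The body of Table 4.2.2-1 is hard to read in the available text, so the treatment-period days come from its footnote. Protocol minus SAP is one recording; SAP minus protocol is none. The SAP has 6 recordings and 5 post-baseline ANCOVA time points. With follow-up added it would have 7 and 6.

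**2. Does other SAP text cover the recording?**

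- The first paragraph of section 3.6.5 refers to the time points specified in the protocol, but it concerns clinic vital signs, not ABPM.
- Section 3.6.4 refers to the treatment and follow-up schedules by name, but for laboratory data.
- Section 3.1 provides for listings, which are neither summaries nor comparisons.
- A version lag is not evident. The SAP (08Sep2017) falls between Amendment 1 (25Jul2017) and Amendment 2 (17Oct2017), and neither table of key changes mentions the follow-up ABPM.

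**3. Is the recording off drug?** Protocol section 3.2.1 gives a half-life of about 8 to 13 hours.

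- At 28 days: 28 × 24 = 672 h; 672/13 = 51.7 and 672/8 = 84 half-lives.
- Across the window: 25 × 24/13 = 46 to 31 × 24/8 = 93 half-lives.

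So yes.

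**4. How precise could the comparison be?** This is context only; the omission does not depend on it. Assume that the prior interval (4.1 to 9.1, n = 19) is a one-group change from baseline and that its SD carries over to ABPM. The protocol states neither.

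- SE = [(9.1 − 4.1)/2] / t(0.95; 18 df) = 2.5/1.734 = 1.44
- SD = 1.44 × √19 = 6.3 bpm
- SE of the difference, 26 v 13 = 6.28 × √(1/26 + 1/13) = 2.13 bpm
- 90% half-width = 1.688 × 2.13 = 3.6 bpm; 95% half-width = 2.028 × 2.13 = 4.3 bpm (36 df)

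For an assumed SD from 5 to 10 bpm, the 95% half-width runs from 3.4 to 6.9 bpm.

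Power by the noncentral t distribution at SD 6.28:

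| True difference at follow-up | α = 0.05 | α = 0.10 |
|---|---|---|
| 6.6 bpm (full persistence) | 85% | 92% |
| 3.3 bpm (half) | 33% | 45% |
| 2 bpm | 15% | 24% |

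These figures assume all 39 subjects have a usable recording. That is a maximum: protocol section 4.1.6 ends follow-up for some discontinued subjects, and the early discontinuation visit (section 4.2.3.1) includes no ABPM.

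**The case against.** The strongest reply has three parts.

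**The SAP may already include the visit.** The ANCOVA sentence speaks of every post-baseline visit and does not repeat the day list, and protocol section 4.8.4.1 sets no limit. On that reading the bracketed list is merely incomplete. This is possible, but the sentence directly follows an explicit list, and a programmer would use the list. An ambiguity here still needs resolving.

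**Follow-up heart rate and blood pressure are covered elsewhere.** This stands in part. Clinic vital signs and ECG are taken at the final visit (Table 4.2.3-1), and SAP sections 3.6.5 and 3.6.6 summarise them by treatment group with change from baseline. A reader might infer that the follow-up ABPM is the only off-drug 24-hour recording, or the only placebo-controlled evidence on reversal. The documents support neither. The Day -2 recording also precedes dosing and is in the SAP list, and the clinic and ECG summaries are by arm in a randomised comparison. What is lost is the 24-hour measure after treatment, with its awake and asleep components.

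**The comparison would be weak.** This also stands in part. A reader might take the 85% power for 6.6 bpm to mean that the visit would settle the question. That figure rests on an assumed SD, on complete data, and on full persistence some 52 to 84 half-lives after the last dose. Partial persistence would usually be missed. This argues for interval estimates rather than for omitting the visit.

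**Conclusion.** The gap is real and narrow. The protocol collects seven ABPM recordings in Cohort 1 and the SAP's list covers six. The missing one is the only 24-hour recording after treatment, from at most 39 subjects (26 on MEDI0382, 13 on placebo), and it serves a secondary safety objective that expressly extends to follow-up. Followed as written, the SAP gives it no summary and no comparison with placebo. This rests on reading the day list in section 3.6.5 as closed, which is the natural reading. It does not rest on the precision figures, which are conditional on assumptions the documents do not confirm.

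Nothing in the documents suggests a decision to discard the recording; an oversight in the list is as likely. No efficacy analysis, sample size or significance level is affected. It is worth correcting before unblinding because the change is nearly free.

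**What to change.** Add the final follow-up visit (28 days after the last dose) to the ABPM visit list in SAP section 3.6.5. Apply the existing by-arm summaries and the change-from-Day -2 ANCOVA to 24-hour, awake and asleep pulse rate, systolic and diastolic blood pressure at that visit. Report the treatment differences as estimates with confidence intervals, give the number of usable recordings per arm, and state that a non-significant difference will not be read as evidence of reversal. If the sponsor prefers to list the recording only, the SAP should say so and give the reason.

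The cost is a wording change and one more visit in an existing table and model. No new data are needed.
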